#### Suicide Risk Management Protocol (SRMP)

The Suicide Risk Management Protocol (**Figure 4**) will be embedded within the online survey tool, which is administered at baseline screening, and the 3-, 6-, and 12-month follow-up time points. It will be triggered on the participant's screen when he/she enters a positive response to the PHQ-9 question, "Over the last 2 weeks, have you had thoughts that you would be better off dead or of hurting yourself in some way?" A positive response also alerts the patient's designated health coach.

[figure not shown]
Upon SRMP initiation, the Scale for Suicide Ideation (SSI) will be activated on the participant's screen via our online survey tool in order to gauge severity of suicide risk. There are skip patterns programmed throughout the SSI so that participants need only complete subsequent parts if they score high enough. Each item is scored on a 3-point scale ranging from 0 to 3 and SSI results are dependent upon the answers submitted.

Parts A and B assess the risk for self-harm. If scores for Part A and B are  $\geq 2$ , the health coach asks about eight established risk factors (Part C). If participants report  $\geq 2$  risk factors, the health coach assesses duration and acuteness of self-harm ideation (Part D and E).

Following completion of the SSI assessment, the health coach will be notified about the participant's automatically assigned risk level for self-harm, which ranges from None to Imminent. Specific actions to be executed by the health coach are outlined depending on the participant's risk level.

If the SSI risk determination is **Moderate** or **High** Suicide Risk, the health coach will enter in a "contract of safety" with the participant where they will agree upon a follow-up call within two hours. Immediately after hanging up

with the participant, the health coach will contact the coordinating site clinical psychologist or designated physician to receive directives on what actions to take. At the agreed upon time, the health coach will call the participant and execute those directives. Alerts will be sent to the designated clinical and research staff contacts at the participant's local site. The health coach will record all events in the SRMP Log.

**Figure 4 - Suicide Risk Management Protocol (SRMP) illustrating risk triggers, assessments, and determinations.**

If the SSI risk determination is **Imminent**, the health coach will keep the participant on the phone line and follow the local site suicide prevention plan or dial 9-1-1 on a second phone line. After, the health coach will follow the procedures for Moderate and High Suicide Risk when appropriate. Alerts will be sent to the designated clinical and research staff contacts at the participant's local site.

Follow-up after Incident:

Health coaches will follow up with participants assigned **Moderate, High, and Imminent** Suicide Risk. The health coach will reach out 1, 3, 7, and 30 days after the incident to see whether suicidal ideation has decreased or been resolved, and whether the participant has followed through with the recommendation provided by the site psychologist.

### 3 OBJECTIVES AND ENDPOINTS

Justification as to why the value of the information to be gained outweighs the risks of participation

OBJECTIVES	ENDPOINTS	JUSTIFICATION FOR ENDPOINTS
Determine whether cCBT will confer greater benefit on daily pain intensity and pain interference at 6 months, compared to m-Education	Daily pain intensity, pain interference	The University of Pittsburgh (Pitt) Sickle Cell Advocacy Team, a group of patient and caregiver partners, identified pain as the primary aspect of SCD that needs more awareness and attention. We also analyzed posts and comments made between Oct. 2012 and Jun. 2016 on the two most popular SCD Facebook groups, Sickle Cell Warriors and Sickle Cell Unite. Of 32,977 messages, 22.5% (7,446) included the word "pain" or "crisis." Sentiment analyses showed that messages with mentions of pain were associated with less social connection and more negative emotions such as anxiety. This study, therefore, will address pain and the socio-emotional needs expressed by the SCD community.
Determine whether cCBT will confer greater benefit on depressive symptoms, health care utilization, and opioid misuse behaviors compared to m-Education	Depressive symptoms, health care utilization (opioid prescriptions, acute care visits), and opioid misuse behaviors (Current Opioid Misuse Measure – COMM)	Mental health is rarely assessed or treated in SCD although 22% to 57% of patients with SCD have clinically significant symptoms of depression, and potentially even more patients suffer from anxiety symptoms. The Sickle Cell Community Consortium (SCCC), led by co-I [name], has identified mental health as a top priority and advocates for educating the community, and routinely screening for mental health symptoms and providing treatment. This study aims to identify how we can fill this gap in SCD care.

This research is necessary to understand the feasibility of a mobile-technology-based behavioral intervention for pain that predominantly targets a minority population. In designing this study we queried 123 adults with SCD using a short online survey to determine if the proposed project objectives and outcomes were relevant and meaningful to patients and their family members. Stress was the most frequently reported modifiable trigger for pain and **88% of respondents wanted to learn about alternatives to taking narcotics for pain**. Ultimately, our

research program will lead to the implementation and dissemination of a cost-effective, acceptable, and effective behavioral intervention to address chronic pain among adults with SCD without the use of opioids, and improve our ability to deliver effective pain treatment to this and other underserved populations.

## 4 STUDY DESIGN

### 4.1 OVERALL DESIGN

CaRISMA is a randomized comparative effectiveness trial among adult patients with SCD who report chronic pain (N = 350) randomized to receive either cCBT (n = 175) or m-Education (n = 175). For at least 12 weeks, one group will be asked to engage in a mobile cCBT program tailored for adults with SCD. The second group will receive pain and SCD education on their mobile phones (m-Education). Both programs use identical mobile-technology platforms; only the content differs. The cCBT program focuses on teaching behavioral coping skills through participants' "seeing and doing" while the pain education arm focuses on improving self-management through participants' "learning and knowing" more about pain and SCD. All participants will have weekly check-ins with a health coach during the first 12 weeks of the intervention and will track pain symptoms daily on the app.

[figure not shown]
**AIM 1:** Compare the effectiveness of two mobile phone-delivered programs—cCBT versus pain and SCD education (m-Education)—for reducing SCD pain symptoms. In a multisite comparative effectiveness trial conducted at five comprehensive sickle cell centers and three CBOs, we will recruit 350 adults with SCD who report chronic pain and randomize them to one of two groups. For at least 12 weeks, one group will be asked to engage in a mobile cCBT program tailored for adults with SCD. The second group will receive pain and SCD education on their mobile phones (m-Education). Both programs use identical mobile-technology platforms; only the content differs. All participants will have weekly check-ins with a health coach during the first 12 weeks and will track pain symptoms daily on the intervention. Our study hypotheses are:

**H1:** cCBT will confer greater benefit on pain outcomes at 6 months, compared to m-Education. Outcomes of this trial will include change in average weekly pain intensity (primary) and pain interference (secondary) at 6 months. As a secondary investigation, we will look at sustainability of the intervention effects at 12 months.

**H2:** cCBT will confer greater benefit on depressive symptoms at 6 months, compared to m-Education.

**H3:** cCBT will confer greater decreases in health care utilization (opioid prescriptions, acute care visits) over 12 months, compared to m-Education.

**AIM 2:** Assess whether baseline depression symptoms moderate the effect of interventions on pain outcomes. Evidence suggests CBT may be particularly helpful for patients with mental health comorbidities. Therefore, we will evaluate heterogeneity of treatment effect (HTE) by mental health status. Subgroup analysis will be conducted by comparing intervention effects between participants with low and high depression. To further understand which intervention works best for whom and when, the lived experience of patients in the trial, and differences in perceptions between depression subgroups, we will do a series of qualitative interviews.

**Figure 1 (repeat) - CaRISMA study design with two interventions arms and 12 months of follow-up for all participants.**

**1st Arm in Study Design: Computerized cognitive behavioral therapy (cCBT) for pain.** The cCBT program will teach users how to recognize negative thoughts and emotions, use cognitive skills and problem-solving, and apply coping behaviors such as distraction, activity scheduling, and relaxation. The cCBT arm emphasizes skills acquisition and learning through practice; thus, the program involves homework assignments and challenges, as well as continued check-ins with a health coach who helps reinforce the CBT skills and encourages practice and program engagement. The cCBT program also give users access to a study-associated Facebook page where they can discuss with other patients issues they faced and what skills were or could be used to address them. This intervention is consistent with the tailored behavioral services patients would receive individually or as a group when working with a psychologist or behavioral pain specialist.

**Table 2 - Summary of module content for the computerized cognitive behavioral therapy (cCBT) in CaRISMA intervention.**

cCBT Content		
Section Number	Title	Education Content
1	Introduction	Intro, SMART Goals, 3Ps pain
2	Biology of Stress	How stress can cause pain or make it worse in sickle cell: Fight or Flight response
3	Relaxation	Relaxation: diaphragmatic breathing, muscle relaxation, imagery, mini relaxation
4	Thoughts and Emotions	ABC Model, automatic thoughts, thought restructuring, distress tolerance, schedule pleasant activities
5	Problem-Solving Skills	Bright IDEAS content, framework for solving everyday problems or challenges
6	Healthy lifestyle & Sleep	Nutrition, Activity (Pacing, graded activity), hydration

**2nd Arm in Study Design: Mobile-delivered pain and sickle cell disease education (m-Education).** The m-Education program will teach users about chronic pain, healthy lifestyle tips (e.g., nutrition and exercise) and facts about SCD.

The emphasis will be on knowledge acquisition and will give users an opportunity to apply what they have learned through brief quizzes and discussion with the health coach and the social network. This program is consistent with the education patients and families would receive with a patient educator or what is currently provided through two of our community partners, Sickle Cell Warriors (SCWarriors) and Sickle Cell 101 (SC101), via the Web and social media.

**Table 3 - Summary of module content for m-Education in CaRISMA intervention**

m-Education Content		
Section Number	Title	Education Content
1	Introduction	Intro to program
2	About sickle cell disease	What is SCD?, terms to know, symptoms and complications to watch out for, heredity
3	Acute and chronic pain	Acute pain, chronic pain, factors that influence pain experience
4	Treatments and medication	About medications, transfusions, pain medications
5	Healthy lifestyle	Diet, exercise, alcohol and drugs, school/work, and hospital stays

### General Study Design

This section describes the role of the clinical team in participant recruitment and the consent process. Also described is participant procedures and involvement in the study. Further information on initial procedures and the recruitment process can be found in **Section 5.5 Strategies for Recruitment and Retention**.

Patient enters Sickle Cell Clinic for routine appointment. During their visit while waiting to be seen, the Research Assistant directs them to the Kiosk where they can learn about CaRISMA.

At the Kiosk, the patient watches the consent video and completes guided prompts to learn about the study. This is followed by a set of study comprehension questions. After informed consent, the patient is asked to complete a set of questionnaires for the baseline measures.

[figure not shown]
Immediately once a patient submits a signed consent form on the Kiosk or electronic web system, the Research Assistant is alerted on their study cell-phone.

In the same clinic visit, the Research Assistant approaches the now-consented patient. Using her own cell-phone or a study provided mobile device, he guides her through downloading the app, interacting with the chatbot, and links her to the CaRISMA Facebook page. In the first use of the chatbot, the patient is randomized based on their study ID into one of two study arms (CBT or Education).

The patient leaves the clinic and interacts with the virtual intervention at her own pace.

Within 24 hours of consenting, one of the health coaches contacts the patient. The health coach informs the patient that they will have weekly one-on-one check-ins throughout the duration of the intervention.

Through text message or email, the patient receives a link to our online survey tool to complete the follow-up questionnaires at 3, 6, and 12-month time points. The patient continues completing modules with the intervention, which includes interactive video lessons.

***Intervention arm is automatically assigned based on the study ID via the mobile app.*** When the CaRISMA program is opened for the first time, it will automatically randomize each participant to either study arm: cCBT or m-Education. It will be 1:1 permuted block randomization to prevent imbalance. Because this is an "open-label" randomized controlled trial (RCT), we will monitor randomization over time to make sure group allocation is similar. The participant will not know which arm they have been assigned to, and they will only have access to the materials included in their respective study arm. Participants will receive a link to our online survey tool where they will be asked to respond to six questionnaires and the Painimation app in order to provide their baseline measures. The six questionnaires are as follows: Sickle Cell Self-Efficacy Scale (SCSES), Patient-Reported Outcomes Measurement information System (PROMIS) Pain Interference, Adult Sickle Cell Quality of Life Measurement Information System (ASCO-ME), Patient Health Questionnaire (PHQ-9), Generalized Anxiety Disorder Scale (GAD-7), and the Current Opioid Misuse Measure (COMM). Painimation is an electronic pain assessment tool developed by our team at the University of Pittsburgh that allows users to better communicate their pain symptoms (**Figure 5**).

[figure not shown]
In addition, our partners at the Qualitative, Evaluation And Stakeholder Engagement (Qual EASE) Research Services will conduct a set of qualitative interviews to further understand which intervention works best for whom and when, the lived experience of patients in the trial, and differences in perceptions between depression subgroups. Qual EASE will randomly select **48 participants** (of the 350) to be interviewed. Attending the qualitative interviews is completely voluntary and participants may opt out at any time. However, if one of the 48 selected participants does opt out, Qual EASE will invite another participant, of those not previously selected, as a replacement.

#### **Baseline.**

Participants will receive a link to our online survey tool where they will be asked to respond to a set of questionnaires and Painimation, a novel pain assessment tool. The questionnaires are as follows: Sickle Cell Self-Efficacy Scale (SCSS), Patient-Reported Outcomes Measurement information System (PROMIS) Pain Interference, Adult Sickle Cell Quality of Life Measurement Information System (ASCO-ME), Patient Health Questionnaire (PHQ-9), Generalized Anxiety Disorders Scale (GAD-7), and the Current Opioid Misuse Measure (COMM). For participants who are eligible to be randomized, in addition to baseline questionnaires, items from the Coping Strategies Questionnaire (CSQ) will be asked through the messaging app as participants progress through their respective program.

The Painimation tool is an electronic pain assessment tool developed by our team at the University of Pittsburgh that allows users to better communicate their pain symptoms. Patients are provided with a selection of animations that they use to describe the quality of their pain. The animations can be increased or decreased in speed, color saturation, focus and size, to reflect the intensity of their pain.

For intervention participants, in addition to the quantitative assessments, our partners at the Qualitative, Evaluation And Stakeholder Engagement (Qual EASE) Research Services will conduct a set of qualitative interviews to further understand which intervention works best for whom and when, the lived experience of patients in the trial, and differences in perceptions between depression subgroups. Qual-EASE will randomly select 48 participants (of the 350) to be interviewed. Attending the qualitative interviews is completely voluntary and participants may opt out at any time. However, if one of the 48 selected participants does opt out, Qual-EASE will invite another participant, of those not previously selected, as a replacement.

**Figure 5** - Screenshot of the Painimation app showing the splash screen, paintable body image, and selection of painimations to indicate quality and intensity of pain.

In the first three months of the study, intervention participants will complete all modules of their assigned study arm (cCBT or m-Education) at their own pace. The recommended progression is one module per week; this will give participants time to practice the techniques taught in each module. Participants will be asked to complete a daily electronic diary to track their pain symptoms.

Only intervention arm participants will receive follow up assessment. The convenience comparison group will not be followed with scheduled assessments.

**1st Follow-Up (T1).** At the end of month 3 (i.e., three months after enrollment, on the same date the participant began the study) participants will again receive a link to our online survey tool to complete the second iteration of Painimation, the SCSS, PROMIS, ASCQ-ME, PHQ-9, and GAD-7. If participants have questions while completing these questionnaires, they may contact their health coach for guidance. Participants will also be asked to complete daily pain intensity entries in the electronic diary. If participants do not complete the questionnaires or the pain intensity entries, health coaches will contact them and remind them to do so. The 48 patients selected for qualitative interviews will have their second interview with Qual-EASE at this time.

Between months 4-6, participants will continue to log their daily pain diary in the CaRISMA intervention but will no longer be expected to have weekly check-ins with their health coach.

**2nd Follow-Up (T2).** At the end of month 6, participants will receive a link to our online survey tool to complete Painimation, SCSES, PROMIS, ASCQ-ME, PHQ-9, and GAD-7 for the third time. Note: participants will not complete the COMM at T2. Though scheduled weekly check-ins with health coaches will have ceased, participants will still have the opportunity to contact their health coach as needed. Participants will continue to complete daily pain intensity entries through the electronic diary.

Between months 6-12, participants will continue daily pain diary submissions and communication with health coaches as needed. Additionally, Qual EASE will conduct the final set of qualitative interviews with the 48 randomly selected participants.

**3rd and final Follow-Up (T3).** In the final month of the study (T3), participants will receive a link to our online survey tool to complete Painimation, SCSES, PROMIS, ASCQ-ME, PHQ-9, GAD-7, and COMM for the final time.

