**Medical Outcomes (PCORnet).**

For patients recruited at one of the five clinical sites, we will evaluate objectively measured opioid medication refills and emergency department visits or hospitalizations for pain crisis. We will be working in collaboration with PCORnet to collect data retrospectively (from the past 12 months) and prospectively (12 months from date of enrollment) from patient medical records. These data will allow us to track medications including opioid pain medication prescriptions and refills, and health care utilization (i.e., emergency department visits and

hospitalizations), as well as lab values (e.g., hemoglobin level) and clinical outcomes (e.g., end-organ damage score). For the patients recruited from our community partner organizations or online who are not affiliated with a participating clinical center, we will only acquire or evaluate their medical records for the purpose of confirming their sickle cell diagnosis.

**Process evaluation measures.** For the intervention to be effective, patients must use the program and acquire coping skills or knowledge about pain and SCD that will help them manage their physical health (e.g., nutrition/exercise), emotional distress, and physiological response to stressors, all factors contributing to pain. As they progress through the intervention, participants will complete elements of the Coping Strategies Questionnaire for sickle cell disease (CSQ) and the Sickle Cell Self-Efficacy Scale (SCSES) shown in **Figure 6**.

1) How sure are you that you can do something to cut down on most of the pain you have when having a pain episode?	Not at all sure	Not sure	Neither	Sure	Very Sure
2) How sure are you that you can keep doing most of the things you do day-to-day?	Not at all sure	Not sure	Neither	Sure	Very Sure
3) How sure are you that you can keep sickle cell disease pain from interfering with your sleep?	Not at all sure	Not sure	Neither	Sure	Very Sure
4) How sure are you that you can reduce your sickle cell disease pain by using methods other than taking extra medication?	Not at all sure	Not sure	Neither	Sure	Very Sure
5) How sure are you that you can control how often or when you get tired?	Not at all sure	Not sure	Neither	Sure	Very Sure
6) How sure are you that you can do something to help yourself feel better if you are feeling sad or blue?	Not at all sure	Not sure	Neither	Sure	Very Sure

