**Table 4. Schedule of interventions and of monitoring patient outcomes.**

Outcome	Measure	Month of Study			
		0	3	6	12
Primary	Pain interference (PROMIS)	X	X	X	X
Secondary	Daily pain intensity (mobile app)	X	X	X	X
	Quality of life (ASCOQ-Me), depression (PHQ-9), anxiety (GAD-7), Painimation	X	X	X	X
	Opioid Use (COMM)	X			X
Medical	Health care utilization (PCORnet): Opioid prescriptions, ED visits, hospitalizations				X
Process Evaluation	Coping (CSQ), Self-efficacy (SCSES)	X	X	X	X
	Program engagement (treatment dose)		X		

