## 5.6 RECRUITMENT PLAN FOR PROSPECTIVE STUDIES

**Table 5** – Recruitment plan including estimated number of eligible patients, total number of participants expected to be approached or screened via the study kiosk and online data capture tool.

Recruitment Plan	
Estimated number of potentially eligible study participants, from prior research and examining medical records: ~400 eligible patients at OSU, UIC and Duke, Hopkins ~200 eligible at Pitt	1600 at clinical sites
Our community-based organizations reach 10000+ patients. Conservative estimate is that 50% of those are eligible adults with chronic pain	5000 through CBO networks
Total number of study participants expected to be approached in clinic (n = 450) or complete online screener (n = 100)	550
Of those screened, total number of study participants expected to be eligible	450
Of those eligible, total number participants enrolled via clinics (n = 300) and CBOs online (n = 50)	350
Target sample size	350
Total number of clinical sites that will enroll participants	5
Projected rate of enrollment	Month 7 start of enrollment
Estimated percentage of participant dropout	10-15% complete no follow-up assessments 30-40% stop using intervention before reaching Module 4

**Table 6.** Estimated final racial/ethnic and gender enrollment table (N = 350)

Race	Male (N)	Female (N)	Total (N)
American Indian/ Alaska Native			
Asian			
Black/African American	170	170	340
Hawaiian/Pacific Islander			
White			
Multirace	5	5	10
Ethnicity	Male (N)	Female (N)	Total (N)
Hispanic (Latino/Latina)			
Non-Hispanic	175	175	350

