## 8 STUDY ASSESSMENTS AND PROCEDURES

### 8.1 ENDPOINT AND OTHER NON-SAFETY ASSESSMENTS

When a potential CaRISMA participant becomes interested in enrolling, they will first be asked to fill out an electronic eligibility screener to confirm inclusion criteria. Immediately after getting accepted into the study, participants will complete separate questionnaires that will serve as their baseline measure. These questionnaires will be completed three more times throughout the course of the study. CaRISMA participants will also complete a daily pain diary throughout the first year of the study.

1. Eligibility Screener: All patients interested in enrolling will be required to complete this online screener to confirm eligibility. It will be accessible at the five clinics for those recruited in-person. A link will be distributed to those recruited online.
2. Coping Strategies Questionnaire (CSQ): Assesses coping in chronic pain patients through item-level factor analysis. Elements of the CSQ will be asked in the chatbot.
3. Sickle Cell Self-Efficacy Scale (SCSES): Assesses the ability of sickle cell patients to function on a day-to-day basis and manage their SCD symptoms.
4. Patient-Reported Outcomes Measurement Information System (PROMIS) Pain Interference Scale: Assesses patient-reported outcomes (physical, mental, and social health) in adults and children
5. Adults Sickle Cell Quality of Life Measurement Information System (ASCO-ME): Measure patient reported outcomes in adults with sickle cell disease.
6. Patient Health Questionnaire (PHQ-9): Assesses the degree of depression severity.
7. Generalized Anxiety Dieorder Scale (GAD-7): Assess the degree of anxiety.
8. Daily pain diary: Participants will log a daily pain diary in the CaRISMA interventions for the entire year of the study.
9. Current Opioid Misuse Measure (COMM): self-reported; monitors indicators of current aberrant drug-related behaviors in patients with chronic pain on opioid therapy. This measure will only be completed at baseline and 12 months.
10. Painimation: an electronic pain assessment tool developed by our team at the University of Pittsburgh that allows users to better communicate their pain symptoms. Patients are provided with a selection of animations that they use to describe the quality of their pain. The animations can be adjusted to reflect the intensity of their pain.

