We will examine the heterogeneity of the treatment effect to determine whether the intervention works better for some than for others. Our prespecified analysis plan will examine differences in pain interference between patients with high (PHQ-9>10) and low (PHQ-9≤10) depression. We will augment the primary analysis models for pain interference with relevant main effects for the baseline depression level and 2- and 3-way interactions with the study arm and time. Of primary interest is the significance of the 3-way interaction (time×study arm×baseline depression level). If significant, we will present the treatment effect estimates and 95% CIs within each subgroup. For all of the above-described models, we will focus on the 6-month outcome.

Mediation Analysis

For coping skills, self-efficacy, and program engagement or dose measures, changes in scores from baseline to 3 months and from baseline to 6 months will be tested as potential mediating variables. We will use the framework of Kraemer et al to calculate effect sizes, accounting for the impact of the potential mediator variable. In addition to modeling each mediator as a function of time, study arm, time×study arm interaction, study site, and baseline depression level (PHQ-9≤10 vs PHQ-9 >10), we will augment the original primary analytic models by including the potential mediator as a covariate.

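### Coping is collected only inside the app after randomisation, so the mediation analysis has no pre-randomisation coping baseline, and later coping values may depend on continued app use

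*Protocol*

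**What the plan says.** **How coping is collected.** Protocol Section 4.1 (Baseline) says that "items from the Coping Strategies Questionnaire (CSQ) will be asked through the messaging app as participants progress through their respective program", in addition to the baseline questionnaires. The process evaluation paragraph of the same section gives similar timing: "As they progress through the intervention, participants will complete elements of the Coping Strategies Questionnaire for sickle cell disease (CSQ". Section 8.1 names the same channel: "Elements of the CSQ will be asked in the chatbot".

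**When randomisation happens.** Section 4.1 (General Study Design) says "In the first use of the chatbot, the patient is randomized based on their study ID into one of two study arms", and a little later "When the CaRISMA program is opened for the first time, it will automatically randomize each participant to either study arm".

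**What is scheduled.** The process evaluation row of Table 4, "Coping (CSQ), Self-efficacy (SCSES", is marked at months 0, 3, 6 and 12. The table does not give the mode of collection.

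**How coping is used.** The Mediation Analysis section of the SAP takes coping skills, self-efficacy and engagement, and tests "changes in scores from baseline to 3 months and from baseline to 6 months" as mediators. Protocol Section 9.4.9 says the same under exploratory analyses.

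**Expected disengagement.** Table 5 in Section 5.6 anticipates that "30-40% stop using intervention before reaching Module 4", and that 10-15% complete no follow-up assessment.

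**The concern.** Coping skill is what the cCBT arm sets out to teach, so it is the natural candidate for explaining any difference between the arms. Analysing change in a mediator needs a starting value that treatment cannot have touched, and later values whose availability does not depend on treatment uptake. The collection route described secures neither.

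If any coping content comes before the first items, part of the arm effect on coping is subtracted out with the baseline. If later items reach only people who still open the app, coping is observed in a group selected by engagement. Engagement is itself a listed mediator and may differ by arm.

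The SAP also enters the mediator as a covariate in the primary model. A likelihood-based mixed model accommodates missing outcomes under its assumptions, but it does not by itself accommodate a missing covariate. The SAP's missing-data section addresses missing outcomes and dropout and gives no rule for a missing mediator.

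**Working it through.** The plan states no figure for this point, so there is none to reproduce. The check compares the relevant sections and then counts.

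**Step 1: can any CSQ item precede randomisation?** The items are asked in the messaging app or chatbot, within the participant's assigned program (Sections 4.1 and 8.1). Assignment is made at first chatbot use or first opening of the program. An item tied to the assigned program must therefore come after allocation. The SAP's Randomization section, which assigns participants once eligibility is complete, does not change this order.

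**Step 2: is there another route?**

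| Place in the protocol | CSQ listed? | SCSES listed? |
|---|---|---|
| Baseline survey questionnaires (4.1) | No | Yes |
| 3-, 6- and 12-month survey batteries (4.1) | No | Yes |
| Completion definition (4.4) | No | Yes |
| Follow-up battery (6.1.2) | No | Yes |
| Required items that prompt coach contact (6.4) | No | Yes |
| Survey links (7.3) | No | Yes |

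The self-efficacy scale (SCSES) shares the Table 4 row and the process evaluation wording with the CSQ, but its survey route is spelled out elsewhere. The CSQ's is not. The SAP describes the SCSES with fixed time points and describes no coping measure.

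**Step 3: timing.** Section 6.1.2 allots 12 weeks for the modules. The 6- and 12-month coping values in Table 4 fall after that period, when collection during progress through the program no longer gives a clear occasion.

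**Step 4: scale, as an illustration.** Inputs are N = 350 and the two Table 5 ranges.

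- Stop before Module 4: 0.30 × 350 = 105 to 0.40 × 350 = 140.
- Still in the program: 350 − 140 = 210 to 350 − 105 = 245.
- No follow-up assessment: 0.10 × 350 = 35 to 0.15 × 350 = 52.5.
- Survey outcomes but no later coping value, if everyone without follow-up is also a stopper: from 105 − 52.5 = 52.5 to 140 − 35 = 105, so about 50 to 105.

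The last line further assumes that those who stop before Module 4 give no later CSQ answers. The documents neither state nor exclude this. Less overlap between the two groups would raise the count towards 105-140; items asked early in the program, or through continued app use, would lower it.

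**The case against.** The strongest reply is that delivery by app does not rule out a schedule. A chatbot can ask items on fixed dates, and Table 4 gives those dates. Participants are asked to keep the diary in the app for the whole year, and coaches encourage engagement after the modules are finished, so completing or stopping modules is not the same as leaving the app. The wording about progress is also weak evidence alone, because it is applied equally to the SCSES, which goes out by survey link. Section 8.1 adds that the baseline questionnaires are repeated three times.

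Much of this stands, and it limits what can be said. A reader might infer the following, and the documents do not support any of it:

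- **That the scheduled coping values will not exist.** The documents leave the route undescribed; they do not show that the values are absent.
- **That the baseline already contains treatment.** Post-randomisation is not the same as post-treatment. Both programs open with an introduction, and Section 6.3 says the introductions look identical. Table 2 does place goal setting and pain content in the first cCBT section, so contamination is possible but not established.
- **That at least 105-140 people lose their later coping values, or that month 6 is missing for nearly everyone.** Both need the item placement, which is not given.
- **That the mediation result is biased by construction.** Size and direction depend on facts outside the documents.

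The reply does not remove the gap. Section 8.1 itself assigns the CSQ to the chatbot, no section gives a pre-randomisation coping value, and a fixed-date chatbot prompt would still reach only people who open the app.

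**Conclusion.** The concern holds as a measurement gap in an exploratory analysis. Followed as written, the plan yields no coping value before randomisation, and it describes no route outside the app for the values that Table 4 schedules. The coping mediation is therefore at risk of a baseline partly affected by program content and of missingness related to engagement.

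The first part follows directly from the text. The dependence of later values on app use is an inference from app-only delivery and from the CSQ's absence from every survey list. The count of about 50-105 rests on the Table 5 rates, on full overlap between the two kinds of dropout, and on stoppers giving no later CSQ answers; it should be quoted only as an illustration.

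Self-efficacy and engagement as mediators do not share this collection gap, and no primary or secondary outcome is affected. The change is worth making because it is cheap, but the trial's main conclusions do not depend on it.

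**What to change.** Add the CSQ items to the online survey at baseline, with completion required before the program is first opened, and to the existing 3-, 6- and 12-month survey links. This gives the values that Table 4 implies. Add the CSQ to the lists in Sections 4.1, 4.4, 6.1.2, 6.4 and 7.3 so that reminders cover it. Treat chatbot answers as process data.

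In the SAP, name the coping measure and its time points, and state how a missing mediator value is handled.

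For participants already enrolled, establish when the first CSQ items were actually asked. Use coping change as a mediator only where they preceded any program content, and report coping missingness by arm and time point. Discarding coping for everyone already enrolled would go further than the documents justify.

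The cost is slightly more participant burden at each survey. The documents do not give the number of CSQ items, so this cannot be sized further. No new contact or visit is needed.
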